12.2.6. Reporting Serious Adverse Events

In order to adhere to all applicable laws and regulations for reporting an SAE(s), the study site must notify Sage and designee within 24 hours of the study site staff becoming aware of the SAE(s). The investigator must complete, sign and date the SAE report form, verify the accuracy of the information recorded on the SAE report form with the corresponding source documents, and send a copy to Sage and designee.

Additional follow-up information, if required or available, should all be sent to Sage and designee within 24 hours of receipt on a follow-up SAE report form and placed with the original SAE information and kept with the appropriate section of the eCRF and/or study file.

Serious adverse events occurring after the designated follow-up time for the study, should be reported to Sage and designee according to the timelines noted above only if the investigator considers the SAE related to IP.

Sage, or designee, is responsible for notifying the relevant regulatory authorities of certain events. It is the principal investigator's responsibility to notify the IRB/IEC of all SAEs that occur at his or her site. Investigators will also be notified of all suspected unexpected serious adverse reactions (SUSARs) that occur during the clinical study. IRBs/IECs will be notified of SAEs and/or SUSARs as required by local law.

12.2.7. Assessment of Liver Biochemistry for Hy's Law Screening, or Hy's Law Laboratory Criteria

Hy's Law is a principle outlining specific criteria to indicate when an individual is at high risk of a severe drug induced liver injury (DILI) as a result of incurring hepatocellular injury sufficient to impair bilirubin excretion.

Potential Hy's Law is defined as [(total bilirubin >2xULN) **AND** alkaline phosphatase <2xULN (any time post-baseline, measured at the same time point of assessment)] **AND** [(ALT or AST >3xULN) **AND** alkaline phosphatase <2xULN, any time post-baseline, measured at the same time point of assessment]. Hy's Law criteria are met if there is no alternative explanation for the elevations in liver biochemistry other than DILI caused by the IP. The elevations of transaminases and bilirubin may occur together or at different time points during the study, therefore, to identify cases of potential Hy's Law, a comprehensive review of liver biochemistry must be performed.

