The investigator is responsible for determining whether a participant meets potential Hy's Law criteria at any point during the study. If a participant has elevations in liver biochemistry, further evaluation may be required and, if elevations meet the potential Hy's Law criteria, it must be reported as an SAE within 24 hours of Investigator awareness (see Section 12.2.6 for procedure on reporting an SAE). All results of laboratory tests including alkaline phosphatase testing should also be appended to the SAE form. The investigator must continue to follow the participant until liver biochemistry returns to normal or baseline levels, or for as long as

clinically indicated. In addition, the investigator should perform any necessary diagnostic evaluations to investigate the etiology of the event and update the SAE report accordingly.

These events must also be recorded as an SAE in the eCRF with the investigator's assessment of seriousness, severity, and causality, and a detailed narrative must be provided on the SAE form. The investigator is responsible for recording data pertaining to potential Hy's Law/Hy's Law cases and for reporting AEs and SAEs in line with standard safety reporting procedures (see Section 12.2.5 and Section 12.2.6).

IP dose modifications for participants who meet potential Hy's Law criteria should be made according to Section 7.4.3.

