8.3. Safety Analysis

Safety and tolerability of SAGE-718 is the primary objective of this study. Proportion of participants experiencing treatment-emergent adverse events (TEAEs) and severity of TEAEs, number of participants who withdraw due to AEs, and change from baseline in vital signs, clinical laboratory analyses, electrocardiograms (ECGs), and responses on the Columbia–Suicide Severity Rating Scale (C-SSRS) are the primary endpoints.

The Safety Set will be used for all safety summary tables by cohort and overall.

The safety endpoints and variables considered in the summary tables for this study are summarized in [Table 2](#).

Table 2: Safety Endpoints and Variables in the Summary Tables

Safety Evaluation	Incidence	Raw Value	Change from Baseline	Normal Range Shift from Baseline	Potentially Clinically Significant	Abnormality/ Clinical Significance
Adverse Events	X					
Clinical Laboratory (Chemistry, Liver function, Hematology,		X*	X	X	X	

Safety Evaluation	Incidence	Raw Value	Change from Baseline	Normal Range Shift from Baseline	Potentially Clinically Significant	Abnormality/Clinical Significance
Coagulation, Urinalysis)						
Physical Exam		*				
Vital Signs		X	X		X	
ECG		X	X		X	*
C-SSRS	X	X		X		

ECG = Electrocardiograms; C-SSRS = Columbia–Suicide Severity Rating Scale
 X = Safety Assessment will be summarized in tables
 * = Safety Assessment will be listed in individual participant data listings

Anytime on treatment, last value on treatment and last value on study will be included in the summaries whenever indicated in the relevant sections as following: Anytime on treatment is defined as measurement on or after first dose, on or before the date of last dose. Last value on treatment is defined as the last post-baseline value between first dose of IP (exclusive) and up to the date of last dose of IP (inclusive). Last value on study is defined as the last post-baseline value on or after the first dose of IP and on or before the last date of the study.

The safety variables evaluated at scheduled visits are taken as done in nominal visit, without any windowing. If a value is available for a nominal scheduled visit, that value will be used in summary by visit. If scheduled visit value is not available, a value from the specific visit window will be included in summary.

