For safety analysis, unscheduled measurements will be included only if a scheduled measurement is not available, and the unscheduled measurement falls within the visit window for the scheduled visit (Table 3). If there are two or more measurements in a visit window, the measurement taken closest to the study day target will be used in analysis. If the two have same distance from the target study day, the latter one will be used.

Table 3: Analysis Visit Window for Safety Analysis

Scheduled Visit	Study Day of Expected Visit	Study Day Window for Visit
Baseline	1	≤ 1
Day 30 (± 7 days)	30	2 to 44
Day 60 (± 7 days)	60	45 to 74
Day 90 (± 7 days)	90	75 to 130

Scheduled Visit	Study Day of Expected Visit	Study Day Window for Visit
Day 180 (± 14 days)	180	131 to 224
Day 270 (± 14 days)	180	225 to 314
Day 365 (± 14 days)	365	315 to 410
Month 15 (± 14 days)	456	411 to 501
Month 18 (± 14 days)	547	502 to 592
Month 21 (± 14 days)	638	593 to 683
Month 24 (± 14 days)	730	684 to 774
Month 27 (± 14 days)	821	775 to 865
Month 30 (± 14 days)	912	866 to 957
Month 33 (± 14 days)	1003	958 to 1048
Month 36 (± 14 days)	1094	1049 to 1139
Month 39 (± 14 days)	1186	1140 to 1231
Month 42 (± 14 days)	1277	1232 to 1321
Month 45 (± 14 days)	1368	1322 to 1413
Month 48 (± 14 days)	1459	≥ 1414

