8.3.2. Clinical Laboratory

Clinical laboratory assessments will include blood samples for hematology, clinical chemistry, coagulation, and urinalysis. Analytes to be evaluated are summarized in [Table 4](#).

All laboratory values will be summarized for the Safety Set by cohort and overall. Results of continuous hematology, clinical chemistry parameters, coagulation, and urinalysis parameters (quantitative) at each scheduled visit and mean changes from baseline will be summarized using standard international (SI) units. In addition, it will also include the summary of anytime on treatment, last values on treatment and last value on study.

All laboratory results will be listed in individual participant data listings.

Results from Hepatitis B and C screening tests, HIV-1 and -2 antibody, CAG test, FSH test at Screening will be listed separately by participant.

Results from urine drug test pregnancy test will be listed separately by participant.

Normal ranges for each parameter will be provided by the laboratory.

Table 4: Summary of Clinical Laboratory Analytes

Biochemistry	Renal Panel: glucose, calcium, phosphorus, blood urea nitrogen, creatinine, sodium, potassium, chloride, bicarbonate Hepatic Panel: albumin, alanine aminotransferase, alkaline phosphatase, aspartate aminotransferase, total bilirubin, direct bilirubin, indirect bilirubin, total protein, lactate dehydrogenase, gamma glutamyl transferase Other: triglycerides, cholesterol (low density lipoprotein [LDL], high density lipoprotein [HDL]), creatine phosphokinase, TSH and reflex to free T3/T4 if TSH is abnormal
Hematology	Red blood cell (RBC) count, hemoglobin, hematocrit, white blood cell count with differential, platelet count, RBC indices (mean corpuscular volume [MCV], mean corpuscular hemoglobin [MCH], and mean corpuscular hemoglobin concentration [MCHC]).
Urinalysis	Protein, glucose, pH, blood, leukocyte esterase, urobilinogen, bilirubin, ketones, nitrite
Coagulation	Activated partial thromboplastin time, prothrombin time, and international normalized ratio
Serology (screening only for Cohort 2 and 3)	Hepatitis B and C screening tests, HIV-1 and -2 antibody

Liver function tests will be monitored closely for potentially clinically significant PCS values, and will be summarized for occurrence anytime post-baseline for the following parameters for these PCS threshold (for condition involving more than one parameter, the results need to be from the same timepoint):

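### SAP 8.3 restricts unscheduled measurements for safety analysis as a whole, which conflicts with the anytime post-baseline liver counts in 8.3.2 and, applied literally, would undercount them

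*SAP*

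**What the plan says.** SAP 8.3 (Safety Analysis) builds its data-selection rules in three steps.

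- It defines the anytime and last-value rows by date. For the first: "Anytime on treatment is defined as measurement on or after first dose, on or before the date of last dose". This does not mention whether a draw was scheduled.
- It sets the by-visit rule: "If a value is available for a nominal scheduled visit, that value will be used in summary by visit". If there is no such value, one from the visit window is used.
- It then turns to unscheduled data: "For safety analysis, unscheduled measurements will be included only if a scheduled measurement is not available", with the further condition that "the unscheduled measurement falls within the visit window for the scheduled visit". Where a window holds several values, proximity decides: "If there are two or more measurements in a visit window, the measurement taken closest to the study day target will be used in analysis".

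SAP 8.3.2 (Clinical Laboratory) says that liver tests "will be summarized for occurrence anytime post-baseline for the following parameters". The thresholds are ALT and AST above 3, 5 and 10xULN, alkaline phosphatase (ALP) and bilirubin above 1.5 and 2xULN, and two combined bilirubin and transaminase criteria, one of them qualified by ALP. Section 8.3.2 does not say whether unscheduled draws count.

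**The concern.** A worst-value count is meant to use every value in its period. The third rule in 8.3 keeps at most one value per window and prefers the scheduled value, or else the one nearest the target day. It never selects the highest.

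The draws at risk are the informative ones. Protocol 12.2.7 requires, for elevated liver tests, that "The investigator must continue to follow the participant until liver biochemistry returns to normal or baseline levels". Protocol 7.4.2 asks for repeat chemistry after a suspected seizure. Protocol 7.4.3 makes resumption of dosing depend on liver results. Much of this testing will fall between scheduled visits. If those results are filtered out, the liver table leans toward showing no signal.

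The table also carries more weight than usual. SAP 6.1 narrows the synoptic report to Day 1, Day 90, Day 180, Day 365 and ET, so the anytime rows are the main tabulated place for a peak between visits.

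**Working it through.** The documents give no expected count of liver events or of unscheduled draws, so there is no planned figure to reproduce. The check applies the rule as written.

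**Inputs.** Visit windows come from SAP Table 3. The laboratory schedule comes from Protocol Tables 2 and 3: in year 1, post-baseline draws fall on Days 30, 90, 180, 270 and 365, with none on Day 60. Thresholds come from SAP 8.3.2. The liver values below are assumed.

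**Step 1: where the rule bites.** The Table 3 windows are contiguous, so every post-baseline draw falls in some window. From Day 2 to Day 410 there are 410 − 2 + 1 = 409 days. The Day 60 window (Days 45 to 74) has no scheduled laboratory draw and covers 74 − 45 + 1 = 30 days. If all scheduled draws are done, an unscheduled draw would be excluded on 409 − 30 = 379 of 409 days, or 92.7%. This is the share of calendar days on which the rule would exclude a draw. It is not the share of peaks lost.

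**Step 2: one participant, both readings.** Assume a scheduled Day 90 draw with ALT 3.4xULN and bilirubin 0.9xULN, then an unscheduled Day 97 draw with ALT 8.2xULN, bilirubin 2.4xULN and ALP 1.3xULN, and all other draws unremarkable. Day 97 lies in the Day 90 window (75 to 130), which already holds a scheduled value.

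| Criterion | 8.3 applied literally | All post-baseline draws |
|---|---|---|
| ALT >3xULN | yes (3.4) | yes (8.2) |
| ALT >5xULN | no (3.4) | yes (8.2) |
| ALT >10xULN | no | no |
| Bilirubin >2xULN | no (0.9) | yes (2.4) |
| Bilirubin >2xULN and ALT or AST >3xULN | no | yes |
| Potential Hy's Law (ALP <2xULN) | no | yes: 2.4 > 2, 8.2 > 3, 1.3 < 2 |

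**Step 3: where a draw survives.** If a similar unscheduled draw falls on Day 50, in the Day 60 window, no scheduled laboratory value competes with it. It enters, and the same criteria are counted. The same holds where a scheduled draw was missed, and at the remote visits (Months 27, 33, 39 and 45), which have no laboratory draw. Even there, only the value nearest the target day is kept if there are several.

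**Step 4: is 8.3 confined to by-visit tables?** Two features say no. The by-visit rule is already complete in the paragraph before, and the next sentence widens the scope from summaries by visit to safety analysis. Also, where the SAP wants unscheduled data it says so, as for the C-SSRS baseline in 8.3.6. Laboratory data get no such wording.

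**The case against.** The strongest reply is that the sentence is by-visit record selection in loose wording. It follows the by-visit rule, refers to Table 3 and leads into a choice of one value per window. None of that suits an anytime summary, which has no target visit. The date-only definition in 8.3, the wording of 8.3.2 and the use of all non-missing data in SAP 8.1.2 all point the other way, and a specific section can be read as overriding a general one. This stands in part. No sentence excludes unscheduled draws from the liver counts by name, and a programmer could follow either reading. A reader might infer that the peaks will certainly be lost, but the documents support only a conflict whose literal resolution loses them.

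The second reply is that cases remain visible. All laboratory results are listed (SAP 8.3.2). A potential Hy's Law case must be reported as an SAE (Protocol 12.2.7) and so reaches the serious TEAE summaries. Other abnormalities become AEs if they meet the conditions in Protocol 12.1.6. This also stands, but listings are not counts, and the SAE route depends on investigator recognition and does not cover an isolated ALT above 3 or 5xULN.

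A reader might also see a contradiction with the protocol, which says that "a comprehensive review of liver biochemistry must be performed". That is a duty to identify cases, and Protocol 12.2.7 makes the investigator responsible for finding them. It is not a tabulation rule, so the SAP does not contradict it.

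**Conclusion.** The point holds as a conflict between SAP 8.3 and 8.3.2. Applied literally, 8.3 leaves an unscheduled liver peak out of the threshold and potential Hy's Law counts when its window already holds a scheduled laboratory value. The consequence is an undercount in the liver table, which could show no case beside a reported SAE. Cases are not lost from the study record.

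The size of the undercount cannot be estimated, because the documents do not say how many unscheduled draws were taken or what they showed. It is tempting to size it by the chance that a scheduled draw meets an elevation of a given length. That measures visit spacing rather than the effect of the rule: many missed elevations would have no draw at all, and no SAP wording recovers those.

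A reader might also infer that a primary endpoint is biased. SAP 4.1 names change from baseline as the primary laboratory endpoint. The liver threshold counts are supporting summaries under the primary safety objective.

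**What to change.** Two edits to the SAP:

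1. In 8.3, limit the rule on unscheduled measurements, and the nearest-to-target choice, to summaries by scheduled visit.
2. In 8.3 and 8.3.2, state that the anytime on-treatment, anytime post-baseline potentially clinically significant and potential Hy's Law summaries use all post-baseline measurements within their stated period, scheduled and unscheduled. Last-value rows continue to follow their date definitions in 8.3.

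The cost is about one sentence in each place and a change to the record-selection flag. The downside is that counts of abnormal values may rise slightly. If the database is already locked, SAP Section 2 requires the change to be documented and discussed in the CSR.

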12.1.7. Columbia-Suicide Severity Rating Scale

Suicidality will be monitored during the study using the C-SSRS ([Posner 2011](#)). This scale consists of a baseline evaluation that assesses the lifetime experience of the participant with suicidal ideation and behavior, and a post-baseline evaluation that focuses on suicidality since the last study visit. The C-SSRS includes ‘yes’ or ‘no’ responses for assessment of suicidal ideation and behavior as well as numeric ratings for severity of ideation, if present (from 1 to 5, with 5 being the most severe).

For de novo participants, the “Baseline/Screening” C-SSRS form will be completed at screening (1 month, 1 year, lifetime), and the “Since Last Visit” C-SSRS form will be completed at subsequent time points ([Table 2](#) and [Table 5](#)). For rollover participants, the “Since Last Visit” C-SSRS form will be completed at the time points outlined in [Table 2](#), [Table 3](#), and [Table 5](#). For 718-CIH-301 v2 Completers, the “Since Last Visit” C-SSRS form will be completed at the Re-Qualification Visit and the Post Re-Qualification Safety Check-in ([Table 4](#)).

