8.3.6. Columbia Suicide Severity Rating Scale

Suicidality data collected on the C-SSRS is collected during the study. The C-SSRS includes ‘yes’ or ‘no’ responses for assessment of suicidal ideation and behavior as well as numeric ratings for severity of ideation, if present (from 1 to 5, with 5 being the most severe).

The participant’s non-suicidal self-injurious behaviors is also assessed separately as part of C-SSRS.

The “Baseline/Screening” C-SSRS form will be completed at screening (lifetime history). The “Since Last Visit” C-SSRS form will be completed at all subsequent time points.

The assessments for suicidal ideation are ranked as follows with 5 being the worst:

1. Wish to be dead
2. Non-specific active suicidal thoughts
3. Active suicidal ideation with any methods
4. Active suicidal ideation with some intent
5. Active suicidal ideation with specific plan

The assessments for suicidal behavior are ranked as follows with 5 being the worst:

1. Preparatory acts or behavior
2. Aborted attempt
3. Interrupted attempt
4. Actual attempt (non-fatal)
5. Completed suicide

Suicidal behavior is considered worse than suicidal ideation.

Baseline for each question is defined as the worst of the assessments done before the first dose of IP, excluding the lifetime version. This will typically include the ‘past 12-month’ version from screening and ‘since last visit version’ from Day 1, as well as any unscheduled visits done before the first dose of IP; any Yes will make the baseline value as Yes.

The number and percentage of participants with at least one response of ‘Yes’ to any C-SSRS suicidal ideation or suicidal behavior item, as well as for Participant’s non-suicidal self-injurious behavior, will be summarized first by visit, then separately for baseline and anytime post-baseline.

Summary of shift from baseline in C-SSRS suicidal ideation and suicidal behavior will be presented for the following categories (no suicidal ideation/behavior, suicidal ideation, and suicidal behavior) for each scheduled assessment time point. If the answer to the first and second assessments in suicidal ideation and all non-missing assessments in suicidal behavior is ‘No’, then the category for the table is considered as ‘No suicidal ideation/behavior’. If any of the assessments in suicidal behavior is Yes, the category is considered as ‘Suicidal behavior’. If any of the assessments in suicidal ideation is Yes but all assessments in suicidal

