- aa All medications, supplements, procedures, and therapies taken within 8 weeks prior to obtaining 718-CIH-301 informed consent will be recorded through the end of the study. All medications, supplements, procedures, and therapies used to treat Huntington's Disease or to treat or prevent COVID, regardless of timing will be recorded through the end of the 718-CIH-301 study.

Table 7: Schedule of Assessments: Additional Visits for 718-CIH-301 v2 Completers

Assessments	Re-Qualification Visit ^{a, b}	Next Scheduled Study Treatment Visit (See Table 8) ^c	Post Re-Qualification Safety Check-in
	Up to 28 days prior to Next Scheduled Study Treatment Visit		
Informed re-consent ^d	X		
Reconfirm inclusion/exclusion criteria ^e	X		
Interim medical history ^f	X		
Optional participant training ^g	X		
Body weight	X		
Body height	X		
Vital signs (including orthostatics) ^h	X		X
Physical examination ⁱ	X		X
Serology test ^j	X		
12-lead ECG ^k	X		X
Safety laboratory assessments ^l	X		X
Urine drug test	X		
Alcohol breath test	X		
Cigarette/tobacco use assessment	X		
Pregnancy test ^m	X		
<hr/>			
C-SSRS (Since Last Visit)	X		X
IP self-administration ⁿ			X
IP adherence monitoring			X
AEs/SAEs ^o	X		X
Prior and concomitant medications and procedures/therapies ^p	X		X

Abbreviations: AE = adverse event; C-SSRS = Columbia–Suicide Severity Rating Scale; ECG = electrocardiogram; eCRF = electronic Case Report Form; HIV = human immunodeficiency virus; IP = investigational product; SAE = serious adverse event.

- a Participants who have completed their Day 395 visit under Protocol Version 2 and wish to continue participation under Protocol Version 3 or higher (“718-CIH-301 v2 Completers”) will return to the site for a Re-Qualification Visit ([Table 7](#)) up to 28 days prior to resuming IP at their Next Scheduled Study Treatment Visit (relative to the date of their Day 1 visit, see [Table 8](#)).
- b Participants who have NOT completed their Day 395 visit under Protocol Version 2 but have completed their Day 365 visit and wish to continue participation under Protocol Version 3 or higher will NOT return to the site for a Re-Qualification Visit. They will return to the site for a Study Continuation Visit (Study Protocol, Appendix 2, Section 20.2) and then continue on to their Month 15 visit (see [Table 8](#)). The participant’s visit schedule should remain relative to the date of their Day 1 visit.

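### By-visit C-SSRS displays keep one form per visit, so a Yes on an unscheduled since-last-visit form can be hidden by a scheduled No; the visit list in SAP 6.1 leaves further forms undisplayed

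*SAP*

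**What the plan says.** SAP 8.3 sets the visit rules for the safety evaluations in its Table 2, and C-SSRS is one of them. For scheduled visits, "If a value is available for a nominal scheduled visit, that value will be used in summary by visit". For the rest, "unscheduled measurements will be included only if a scheduled measurement is not available", and then only if it falls in the visit window. With several measurements in a window, "the measurement taken closest to the study day target will be used in analysis"; the worst is not taken and they are not combined.

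SAP 8.3.6 departs from this before dosing only: "Baseline for each question is defined as the worst of the assessments done before the first dose of IP", and this takes in screening and Day 1 forms "as well as any unscheduled visits done before the first dose of IP; any Yes will make the baseline value as Yes". After baseline the since-last-visit "C-SSRS form will be completed at all subsequent time points". Protocol 12.1.7 describes that form as "a post-baseline evaluation that focuses on suicidality since the last study visit".

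SAP 8.3.6 plans these displays:

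- Yes responses by visit, at baseline and any time post-baseline
- a three-category shift at each scheduled time point
- an any-time shift in maximum ideation rank
- a bar graph over time
- a listing

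SAP 6.1 says the synoptic report focuses on Day 1, Day 90, Day 180, Day 365 and ET.

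**The concern.** One value per visit is a reasonable choice for a point measurement such as blood pressure, because the dropped reading and the kept reading estimate the same thing. The post-baseline C-SSRS is different: each form reports on an interval, and the next form starts where the last one ended. Dropping a form therefore removes an interval that no other form in the display covers.

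Change in C-SSRS responses is part of the primary endpoint. A reader who looks at the by-visit table, or at the only shift table with a behavior category, may see no suicidality at a visit although a Yes was recorded in the interval that the column seems to describe.

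**Working it through.** The plan gives no rate or power figure on this point, so there is none to reproduce. The check uses the rule text and look-back arithmetic on nominal days.

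**1. Does the rule reach C-SSRS?** Yes. C-SSRS is in SAP Table 2, and 8.3.6 makes an exception for baseline but none after it.

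**2. What happens to an unscheduled form.** Inputs: scheduled forms on Days 1, 30, 60, 90, 180, 270 and 365 (SAP Appendix A, Table 5, Cohort 2), and windows of 75 to 130 for Day 90 and 131 to 224 for Day 180 (SAP Table 3). Let u be the day of the unscheduled form, p the scheduled form before it and s the one after it. The days covered only by the dropped form are u − p, and their share of the interval is (u − p)/(s − p). With p = 90 and s = 180:

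| u | Falls in window of | Displaced by | Days not covered | Share |
|---|---|---|---|---|
| 120 | Day 90 | Day 90 form | 120 − 90 = 30 | 30/90 = 33% |
| 135 | Day 180 | Day 180 form | 135 − 90 = 45 | 45/90 = 50% |
| 140 | Day 180 | Day 180 form | 140 − 90 = 50 | 50/90 = 56% |
| 170 | Day 180 | Day 180 form | 170 − 90 = 80 | 80/90 = 89% |

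These are recall days for chosen examples, not event risks.

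**3. What the visit list in SAP 6.1 leaves out.** The look-backs of the Day 30, 60, 90, 180, 270 and 365 forms are 29, 30, 30, 90, 90 and 95 days, which total 364.

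- Displayed (Days 90, 180, 365): 30 + 90 + 95 = 215, and 215/364 = 59.1%.
- Not displayed (Days 30, 60, 270): 29 + 30 + 90 = 149, and 149/364 = 40.9%.

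The Cohort 1 row reads differently at Days 1 and 30 in the two documents, possibly from text extraction. The total does not depend on it: without a Day 30 form, the Day 60 form looks back 59 = 29 + 30 days.

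**4. The additional visits.** The Study Continuation form can fall as late as Day 395 + 7 = 402, inside the Day 365 window (315 to 410). The Re-Qualification form is taken up to 28 days before the visit at which treatment resumes, and the Check-in form 23 to 37 days after it. At nominal days:

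| Resumption visit | Earliest Re-Qualification | Latest Check-in | Window |
|---|---|---|---|
| Month 15 | 456 − 28 = 428 | 456 + 37 = 493 | 411 to 501 |
| Month 18 | 547 − 28 = 519 | 547 + 37 = 584 | 502 to 592 |
| Month 21 | 638 − 28 = 610 | 638 + 37 = 675 | 593 to 683 |
| Month 24 | 730 − 28 = 702 | 730 + 37 = 767 | 684 to 774 |

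If these forms are read as extra in-window values, the scheduled form displaces them. If they are read as nominal visits in their own right, SAP 6.1 does not list them. They are absent from the by-visit displays either way.

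**5. Which displays are affected.**

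| Display (SAP 8.3.6) | Keeps a displaced Yes? |
|---|---|
| By-visit incidence | No |
| Three-category shift by scheduled time point | No; baseline is worst of all forms, post-baseline is one form |
| Bar graph over time | Probably not; derivation not specified |
| Any-time post-baseline incidence | Should |
| Any-time maximum-rank ideation shift | Should; maximum against maximum |
| Listing | Should, with its date |

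**The case against.** The strongest reply is that nothing disappears from the report. The any-time incidence and the any-time ideation shift should include the response, and SAP 8.1 has listings sorted by visit and date, so the timing is there too. The report is purely descriptive, no schedule plans unscheduled post-baseline C-SSRS forms, and the count of such forms could be zero. This stands, and it limits the size of the point.

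Several stronger readings are tempting, and the documents do not support them:

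- *Both shift tables are lopsided.* Only the three-category table is; the any-time ideation shift compares like with like.
- *The shift must lean heavily toward improvement.* Exclusion 20 bars Cohorts 1 and 2 from entry with suicidal behavior, or ideation item 4 or 5, since the last visit, and Cohort 3 was not enrolled. Little baseline behavior should exist to improve from. The likelier effect is that a new Yes goes unseen.
- *The unscheduled-measurement rule removes the Re-Qualification, Check-in and Study Continuation forms.* Those visits are planned in the protocol. The main reason they are not displayed is SAP 6.1.
- *Unscheduled forms are mostly positive, so the bias can be put as a percentage.* The documents give neither the number of such forms nor their results.

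The reply does not repair two things. The any-time shift covers ideation only, so behavior has no shift table that uses all forms. And the sentence on unscheduled measurements is worded for safety analysis in general, while 8.3 defines any time on treatment but not any time post-baseline. A programmer could drop unscheduled forms from the any-time rows as well.

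**Conclusion.** The point holds for the by-visit incidence table and the three-category shift, and probably for the bar graph. Under the stated rule, a recorded Yes on an unscheduled form is shown as No whenever the scheduled form for that window exists and is No. Separately, with displays at Days 90, 180 and 365, 149 of 364 nominal first-year days (40.9%) are covered only by forms that are not displayed by visit.

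The effect on displayed rates cannot be computed. Each affected participant lowers a by-visit percentage by 1/156 = 0.6 percentage points if all 156 planned rollovers were treated; the documents do not give the actual number.

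The conclusion rests on three assumptions: an unscheduled C-SSRS contact counts as a study visit and so restarts the recall period; the visit list in 6.1 governs the 8.3.6 displays; and the any-time summaries use all forms. A reader might infer that suicidality reports are lost from the study. The planned any-time summaries and the listing do not support that.

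**What to change.** Add a rule to SAP 8.3.6 along these lines:

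> For by-visit C-SSRS displays, all Since Last Visit forms (scheduled, additional or unscheduled) dated after the previous displayed visit, up to and including the current displayed visit, are combined. An item is Yes if it is Yes on any of them. The one-value-per-visit rule in 8.3 does not apply to C-SSRS. Any-time post-baseline summaries use all post-baseline forms, including unscheduled and additional ones. Forms that look back over an off-drug gap are shown under their own label.

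The interval must run from the previous *displayed* visit. Pooling only from the previous scheduled visit would still leave the Day 30, 60 and 270 forms, and forms after Day 365, out of the reported columns. With the rule as worded, the Day 90, 180 and 365 columns cover 364 of 364 nominal first-year days. The derivation of the bar graph should be stated at the same time.

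The cost is SAP wording and a small derivation change, with no new data. The columns then represent intervals of unequal length and must be labelled so, and displayed rates may be slightly higher. Forms with no later displayed visit, such as the Safety Follow-Up form after ET, would still appear only in the any-time summaries and the listing.
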